The protocol, informed consent form(s), recruitment materials, and all participant materials will be submitted to the Institutional Review Board (IRB) for review and approval. Approval of both the protocol and the consent form must be obtained before any participant is enrolled. Any amendment to the protocol will require review and approval by the IRB before the changes are implemented to the study. In addition, all changes to the consent form will be IRB-approved; a determination will be made regarding whether a new consent needs to be obtained from participants who provided consent, using a previously approved consent form.

1 PROTOCOL SUMMARY

1.1 SYNOPSIS

Title:	Task-dependent effects of TMS on the neural biomarkers of episodic memory
Study Description:	The Behavioral Neurology Unit studies the human brain systems underlying learning and adaptation with the goal of finding interventions to make these processes more efficient. In this study, we are interested in examining how the task state of the episodic memory network influences the effect of facilitatory TMS on memory and its EEG neural correlates. It is hypothesized that Network-targeted parietal-TMS will improve memory performance and enhance EEG biomarkers of successful memory performance, but that these changes will be modulated by the ongoing task activity during stimulation.
Objectives:	
Primary Objectives:
 
 Investigate how TMS modulates EEG neural measures of successful memory and the association of this modulation with behavioral performance Examine how memory task state influences susceptibility to plasticity via TMS and determine the optimal neural state for improving memory 
Exploratory Objectives:
 
 Search for MRI predictors of the effects of TMS
Endpoints:	
 Primary Endpoints: Memory performance, Late Positive Posterior ERP, evoked theta/alpha power (secondary), EEG functional connectivity (secondary) Exploratory Endpoints: fMRI resting state functional connectivity, fractional anisotropy
Study Population:	32 Healthy Volunteers ages 18-40. Referrals will occur from the NIH Clinical Research Volunteer program or through self-referrals to the protocol.
Description of Sites/Facilities:	Protocol activities will occur at the OP5 clinic and 7SW clinic at the NIH clinical center.
Enrolling Participants:	50 Healthy Volunteers ages 18-40

Abbreviated Title: Task-dependent TMS and memory

Version Date: 11.15.22

Study Duration: 60 months

Participant Duration: 1 month

Abbreviated Title: Task-dependent TMS and memory
Version Date: 11.15.22

1.2 SCHEDULE OF ACTIVITIES (SOA)

Procedures	Enrollment/Screening Day -7 to -1	Baseline Visit 1, Day 1	Study Visit 2 Day 4 +/-3 day	Final Study Visit 3 Day 13 +/-8 day
Informed consent	X			
Demographics	X			
Medical history	X			
Concomitant medication review	X			
Physical exam	X			
Vital signs	X			
Height	X			
Weight	X			
3T MRI		X		
EEG			X	X
TMS			X	X
Cognitive Tasks			X	X
Pregnancy test ^b		X		
Complete Case Report Forms (CRFs)				X

a:
b: Urine pregnancy test (women of childbearing potential).

2 INTRODUCTION

2.1 STUDY RATIONALE

The Behavioral Neurology Unit studies the human brain systems underlying learning and adaptation with the goal of finding interventions to make these processes more efficient. This study will observe neural reorganization underlying episodic memory performance. The protocol will investigate how engaging in a memory task alters the activity and connectivity of the network and the relevance of those changes to successful task performance. Also, how this adaptation influences plasticity of the network will be examined. Using simultaneous TMS, EEG, and cognitive testing, this study will examine the network basis of memory processing, as well as elucidating potential mechanisms of TMS-induced memory improvement.

The overall objective of this study is to (1) examine the effects of TMS on EEG biomarkers of successful memory performance and (2) investigate how the task state of the episodic memory network influences the effect of facilitatory TMS on memory.

The results will answer basic science questions about the network basis of memory processing, with potential application to other cognitive networks and domains. Additionally, these data will provide a greater understanding of TMS as a tool for influencing the hippocampus, the network, and memory performance, allowing for optimization of stimulation for that purpose. Finally, this work will address clinical questions on how to improve memory and re-channel activity in networks via noninvasive stimulation for clinical purposes.

2.2 BACKGROUND

Episodic memory provides a means by which we reflect on the past, make decisions about the future, and form a learned identity. Deficits in this system occur in a variety of neurological and psychiatric disorders¹⁻⁵, making them one of the most debilitating problems in neurology^{6,7}. However, there currently exist no effective treatments for memory impairment. A better understanding of how the brain adapts to perform a memory demand will not only expand our basic knowledge of memory processing but could inform novel treatments for individuals with memory impairments.

Episodic memory depends on the hippocampus^{8,9} and a distributed set of regions which form the hippocampal-cortical network (HCN), including medial prefrontal, posterior cingulate, and medial and lateral parieto-occipital cortex¹⁰⁻¹³. This network shows changes in fMRI activity and connectivity in response to successful memory encoding and retrieval¹⁴⁻¹⁸. Likewise, abnormal function of this network has been associated with memory impairment in many disorders, including traumatic brain injury^{19,20}, epilepsy^{21,22}, and Alzheimer's disease^{23,24}. Additionally, the HCN generates real-time EEG signatures of successful encoding and retrieval, most notably the Late Positive Posterior Event-Related Potential (ERP)²⁵ and oscillatory activity in the theta/alpha band²⁶.

There has been substantial recent interest in using brain stimulation to manipulate brain networks, both to test the role of particular regions and networks in memory processing causally and as a potential therapeutic tool in treating memory disorders²⁷⁻²⁹. Noninvasive transcranial magnetic stimulation (TMS) has been used to manipulate activity and connectivity in the HCN and improve memory performance in healthy adults³⁰⁻³⁹. Repeated treatment over days produces

Abbreviated Title: Task-dependent TMS and memory

Version Date: 11.15.22

lasting effects³⁰⁻³⁶, but single sessions of cTBS have been effective^{37,38} and time-locked cTBS can produce facilitation at the trial-by-trial level³⁹. However, while enhancement of connectivity in the HCN is positively correlated with memory improvement, how TMS treatment increases the retention of information in the HCN and particularly the hippocampus remains unknown. Additionally, while the effects of time-locked cTBS have been examined in relation to fMRI activity in the hippocampus³⁹, the effect of HCN cTBS on EEG measures of successful memory has not been studied. Establishing these mechanisms will improve the basic understanding of how the brain successfully meets a memory demand and inform translational studies for the treatment of memory impairment. One goal of this project is to examine the effects of on-line TMS on the electrophysiological signatures of successful memory performance to provide more information on the mechanism by which TMS improves episodic memory to develop new and specific biomarkers of target engagement for future clinical studies.

The effects of brain stimulation have been shown previously to vary depending on neural state, such as the phase of oscillations relevant to the stimulated network^{40,41} and network activation by simultaneous task performance⁴²⁻⁴⁴. However, the influence of brain state on HCN facilitation with TMS has not been investigated, despite its likely importance. A second goal of this project is to examine this question of task state-dependent modulation for the HCN and episodic memory.

Using simultaneous EEG, TMS, and memory testing, we will investigate the EEG activity related to successful memory performance and examine how TMS modulates that activity. In healthy volunteers, we will deliver brief, facilitatory TMS before and during the encoding trials of a memory task to either the HCN, via an inferior parietal cortex site with maximal hippocampal connectivity, or to the vertex as a control. We will additionally deliver stimulation during a control task with similar attentional demands and processing load, and there will be a no-stimulation condition for both tasks. We will record task performance and time-locked EEG activity, focusing on episodic memory performance and the late positive posterior ERP, theta/alpha power, and EEG functional connectivity measured during encoding and retrieval as our outcome measures.

2.3 RISK/BENEFIT ASSESSMENT

2.3.1 Known Potential Risks

TMS

Brief, self-limited, seizures were seen in early studies, before limits were established for combinations of delivery parameters and still occur occasionally. However, this risk has been reduced to the order of one in every 50,000 sessions in individuals without specific risk factors. For TMS, safety guidelines have been developed⁴⁵ and updated⁴⁶. These guidelines were incorporated into FDA's Class II Special Controls Guidance Document: Repetitive Transcranial Magnetic Stimulation (rTMS) Systems in Table 2. Maximum Safe Train Duration (seconds) Limits for Avoiding Seizures. Furthermore, the study participants are a lower risk since participants with any neurological or psychiatric disorders, history of seizure or taking certain medications are excluded. cTBS was not included in the guidelines. However, there is only a

Abbreviated Title: Task-dependent TMS and memory

Version Date: 11.15.22

single report of seizure with cTBS⁴⁷. In that single patient, the study was conducted in at stimulation intensity levels higher than in this study.

TMS has been found to produce hearing loss in experimental animals, caused by the click produced by the stimulating coil. However, no evidence of chronic hearing loss when hearing protection was used, in several normal participants who had been extensively studied with TMS was found, nor transient changes in several participants tested before, and immediately after stimulation⁴⁸ and more recent has found no increase in auditory threshold from TMS^{49,50}. All participants will wear earplugs to reduce the risk of cochlear damage.

Other than this, TMS does not appear to pose any hazard beyond that of electrical brain stimulation, which has been in clinical use for decades.

Behavioral measures

There are no major risks associated with these memory tests other than frustration or embarrassment associated with the participants' performance.

EEG

There are no major risks associated with EEG recording, however there is a possibility of discomfort from the electrode cap and abrading of the scalp during electrode application. Additionally, there may be electrode gel remaining in the hair following cap removal.

MRI

People are at risk for injury from the MRI magnet if they have pacemakers or other implanted electrical devices, brain stimulators, some types of dental implants, aneurysm clips (metal clips on the wall of a large artery), metallic prostheses (including metal pins and rods, heart valves, and cochlear implants), permanent eyeliner, implanted delivery pump, or shrapnel fragments. Welders and metal workers are also at risk for injury because of possible small metal fragments in the eye of which they may be unaware. People with fear of confined spaces may become anxious during an MRI. Those with back problems may have back pain or discomfort from lying in the scanner. The noise from the scanner is loud enough to damage hearing, especially in people who already have hearing loss. Participants will be fitted with ear plugs. There are no known long-term risks of MRI scanning.

Procedures to Minimize Risk

TMS

Study staff will be trained in TMS administration, TMS safety, and the measurement of the TMS-evoked potentials by [name]. Study staff will be trained to recognize and

Abbreviated Title: Task-dependent TMS and memory

Version Date: 11.15.22

respond to signs of seizure and syncope. For each session, at least two TMS-trained personnel will be in the laboratory. A licensed independent practitioner (LIP), a physician or nurse practitioner trained in TMS, will be in house, specifically aware of the session, and reachable by phone for all TMS sessions. The TMS laboratory is in a clinic area with nursing and code team support. Each room has oxygen, suction, and an emergency call button. If a participant has a significant event, such as a seizure, the hospital emergency system (Code Blue) will be activated and treatment will be initiated as required.

Study staff will monitor individuals during participation and participants will be encouraged to tell experimenters of any discomfort. At each session, participants will be asked whether stimulation was (1) tolerable, (2) tolerable with some discomfort, or (3) intolerable. If the participant responds that stimulation is intolerable, the participant will be withdrawn from the experiment. Any participant exhibiting distress or who wishes to stop the experiment for any reason will be allowed to stop. Nonprescription drugs may be used to alleviate headache or pain discomfort.

Persons operating TMS equipment will have been certified by a NINDS TMS laboratory or the NIMH Noninvasive Neuromodulation Unit (NNU) in safe application of TMS.

Standard training procedures used include training in TMS device operation, supervised repeated practice in TMS procedures, and testing for inter-rater reliability in motor threshold determination. To be credentialed as a TMS user, an individual must have passed the following criteria, as assessed by senior BNU or NNU staff:

- 1) Training in TMS device operation
- 2) Supervised administration of at least 10 TMS procedures
- 3) Demonstration of inter-rater reliability on motor threshold determination
- 4) Current Basic Life Support certification
- 5) Training on basic TMS safety and risks by TMS-trained physician
- 6) Training on recognition and initial response to seizures

Behavioral measures

To minimize the risk associated with frustration or embarrassment, the researcher will maintain a positive attitude and observe the participants' behavior to determine if they are overly frustrated. Breaks will be at participant's request.

EEG

To reduce discomfort during electrode application, the researcher will use care in securing the cap for comfort and in moving hair to clear access to the scalp. Additionally, after cap removal, participants will be provided with shampoo and sink space to clean gel from their hair should they desire.

MRI

To mitigate the risk of damage associated with exposure to a powerful magnet, all magnetic objects (for example, watches, coins, jewelry, and credit cards) must be removed before entering the MRI scan room. In addition, participants will be screened for metal implants such as pacemakers or other implanted electrical devices, brain stimulators, some types of dental implants, aneurysm clips (metal clips on the wall of a large artery), metallic prostheses (including metal pins and rods, heart valves, and cochlear implants), permanent eyeliner, tattoos posing MRI risk, implanted delivery pump, or shrapnel fragments.

To minimize the risk of hearing damage, participants will be given earplugs or noise reducing headphones. To confirm that our female participants are not pregnant, thus removing any unknown risks of MRI on a fetus, women of childbearing potential will have a urine pregnancy test within 24 hours of participation in the fMRI experiment. Female participants will not be allowed to participate if the test is positive. There are no risks of pregnancy testing.

2.3.2 Known Potential Benefits

This study does not offer direct benefit to participants but is likely to yield generalizable knowledge about TMS and the effects on memory.

2.3.3 Assessment of Potential Risks and Benefits

Brief, self-limited, seizures were seen in early studies, before limits were established for combinations of delivery parameters and still occur occasionally. However, this risk has been reduced to the order of one in every 50,000 sessions in individuals without specific risk factors. Extensive training will be administered by [name], a neurologist and an expert in TMS, so study staff can effectively recognize and respond to adverse effects. Additionally, a licensed independent practitioner (LIP), a physician or nurse practitioner trained in TMS, will be in house, specifically aware of the session, and reachable by phone for all TMS sessions.

Although this risk is more than minimal, the information to be gained is of great benefit. Episodic memory deficits occur in a variety of neurological and psychiatric disorders¹⁻⁵, making them one of the most debilitating problems in neurology^{6,7}. However, there currently exist no effective treatments for memory impairment. TMS has shown promise as a method of improving memory in healthy adults³⁰⁻³⁹, including older adults⁵¹. A better understanding of the effects of this tool on memory processing could inform novel treatments for individuals with memory impairments.

3 OBJECTIVES AND ENDPOINTS

OBJECTIVES	ENDPOINTS	JUSTIFICATION FOR ENDPOINTS
Primary		
1. Investigate how TMS modulates EEG	1. Memory performance	1. Memory performance measures will allow us to

[figure not shown]
OBJECTIVES	ENDPOINTS	JUSTIFICATION FOR ENDPOINTS

neural measures of successful memory and the association of this modulation with behavioral performance
 
2. Examine how memory task state influences susceptibility to plasticity via TMS and determine the optimal neural state for improving memory
	
 • Accuracy: Percentage of successful (later remembered hit and correct rejection) vs unsuccessful (forgotten miss and false alarm) trials for item recognition (remember/familiar/new) and context recollection (spatial location) • d': Analysis of hits (correctly remembered as encoded) relative to false alarms (new objects labelled as encoded) for item recognition 
2. Late positive posterior ERP
 
 • ERP amplitude 500-700 ms after trial onset (encoding and retrieval) over parietal and occipital electrodes 
3. Theta/alpha power (secondary)
 
 • Power in the 4-13 Hz band 0-1000 ms after trial onset (encoding and retrieval) 
4. EEG functional connectivity (secondary)
 
 • Pearson correlation coefficients (r) between electrode time courses after trial onset (encoding and retrieval) 	
examine the effects of TMS on performance, as well as to sort successful vs unsuccessful trials for EEG analyses
 
2. The late positive posterior ERP has been previously shown to be a robust marker of successful memory performance²⁵
 
3. Task-induced changes in this frequency band have been previously associated with successful memory performance²⁶
 
4. fMRI functional connectivity modulation via network-targeted TMS has been previously associated with TMS-induced memory improvement. Whether EEG functional connectivity will be similarly altered, and the relevance to memory changes, remains unknown

Tertiary/Exploratory		
1. Search for MRI predictors of the	1. Baseline fMRI functional connectivity	It is hypothesized that TMS influences downstream targets

OBJECTIVES	ENDPOINTS	JUSTIFICATION FOR ENDPOINTS
effects of parietal TMS	
 Resting state functional connectivity at baseline between the hippocampus and cortical regions Baseline DTI structural connectivity Fractional anisotropy (FA) at baseline between the hippocampus and cortical regions 	(i.e., regions other than the stimulation site) via network connections. Associations between TMS outcomes and structural or functional connectivity would support this hypothesis, elucidating potential mechanisms of TMS effects

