4 STUDY DESIGN

This protocol is a single site study. The study will include a baseline 3T MRI session, and two experiments conducted during two sessions of simultaneous TMS, EEG, and cognitive testing (Figure 1). Both experiments will use the same participants to allow for within-subjects comparisons and the order of experiments will be counterbalanced. Participants who miss a session will be rescheduled or replaced (see Recruitment). Participants will make three visits to the lab, a baseline assessment session and two TMS/EEG sessions, for a time commitment of approximately 8 hours. TMS/EEG Session 1 will occur 1-31 days following the baseline visit and TMS/EEG Session 2 will occur 4-31 days following TMS/EEG Session 1 (Figure 1).

Figure 1. Study Design

[figure not shown]
On each TMS/EEG day, participants will undergo EEG recording using a 64-channel elastic cap. During recording, they will complete two blocks of a task, one for each experiment, which differ only in their timing of TMS delivery. Each block consists of 90 study trials of episodic memory encoding (45 trials) and spatial processing (45 trials) for a total of 180 trials (90 memory and 90 spatial processing) per TMS/EEG session (Table 1).

Table 1. Conditions and trial counts.

	Parietal Stimulation				Vertex Stimulation				TOTAL			
	Stim On		Stim Off		Stim On		Stim Off					
	Memory	Spatial	Memory	Spatial	Memory	Spatial	Memory	Spatial				
Experiment 1	30	30	15	15	30	30	15	15	180	360		
Experiment 2	30	30	15	15	30	30	15	15	180			

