TMS will be paired with task trials and consist of 2-second trains of continuous theta burst stimulation (cTBS; see Study Procedures). In Experiment 1, TMS will be delivered during the rest phase immediately prior to trial onsets (Figure 2). In Experiment 2, TMS pulses will occur during the trial while participants are actively engaged in the task (Figure 2). The order of experiments will be counterbalanced across subjects within each session. TMS will be delivered to an episodic memory network-connected location in posterior parietal cortex (see 4.4.2. TMS, below) or to the vertex as an inactive control condition, and the order of stimulation location will be counterbalanced across TMS/EEG sessions. One-third of trials will contain no stimulation as an additional control to examine behavioral and neural effects in the absence of the TMS sensory artifact (Table 1). Participants will then be tested on encoded items, also with EEG recording. EEG data will be examined in an event-related design, with timeseries following trial onsets compared across task (memory encoding, spatial processing, and memory retrieval) and stimulation (parietal-TMS, vertex-TMS, and no-TMS) conditions.

Figure 2. Experiment Design

Recruitment

Healthy participants will be recruited from the pool of individuals self-referring to the study directly and via the NIH Clinical Research Volunteer Program and via advertisements that will be pre-approved by the IRB. Although NIH employees will be allowed to participate, no direct solicitation of employees/staff by supervisors or co-workers will take place. Any recruitment material will be IRB approved. Participants who indicate interest will be pre-screened by phone. Pre-screening questions are listed in Appendix B. IRB-approved ads will be posted on NIH listservs with the permission of the moderator and IRB required statement on how the receiver was identified. Listservs may include NIH sponsored recruitment list serves such as (NIH HV recruitment list serv). Listserv announcement will include:

“You are receiving this message because your email address is included in the above NIH Listserv mailing list. The purpose of this message is to inform you of studies that are recruiting

Abbreviated Title: Task-dependent TMS and memory

Version Date: 11.15.22

volunteers at NIH, Bethesda, Maryland. The moderator of the listserv mailing list has permitted its use for this distribution”.

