It is possible that some participants will miss a session. If this occurs, and the participant is still willing to participate, we will reschedule. If a participant no longer wishes to continue with the study, a new participant will be recruited for the full study. If they have data from one experiment, those data will still be included in analysis for that experiment but excluded from any comparisons across experiments.

It is possible that technical problems may arise. If this occurs, and the participant is willing to continue with the study, we will reschedule.

Screening

Participants who pass pre-screening will be invited to participate in the study and scheduled for consent and formal screening.

Upon arrival to the screening appointment, written, informed consent will be obtained by an investigator and formal screening will be done according to Appendix A.

Volunteers who have not had a neurological exam from an NINDS provider within the past two years will receive a neurological examination from an NINDS physician or nurse practitioner. This will not replace any exam the participant will receive for purposes of medical care; the exam will be for research purposes only. All women of child-bearing potential will have a urine pregnancy test (not earlier than 24 hours) before each MRI scan.

In some cases, consent, screening, and examination (when required) may be performed on the same day as the baseline MRI.

Study procedures:

Behavioral Tasks

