Memory Task: This is a test of episodic memory, including item recognition and context recollection^{30,52,53}. In the task, participants will be shown a series of objects in one of four quadrants on the screen. They will be instructed to remember the objects and where they were located, both of which will be tested later. To ensure attention and for consistency with the spatial task (see below), they will be asked to indicate by button press whether the object is primarily used outdoors (e.g., a baseball) or indoors (e.g., a television). During the encoding phase, each object will be presented for 4 seconds with 4 seconds between trials. In Experiment 1, TMS will occur during a 2 second cue before each trial and in Experiment 2, TMS will occur in the first 2 seconds of stimulus object presentation. There will be 180 encoding trials, interspersed with 180 trials of the spatial task (described below). Trial order will be randomized. The retrieval phase will occur following the end of encoding. Participants will be shown, sequentially and in randomized order, the 180 encoded objects and 180 new lure objects, for a total of 360 trials. For all trials, they will respond with whether the object was old (previously seen) or new (not previously seen) and their confidence on a scale of 1-6 (1=confident new,

Abbreviated Title: Task-dependent TMS and memory

Version Date: 11.15.22

6=confident old) as a measure of item recognition. If the object was previously seen, participants will then be asked which quadrant the item was presented in to provide a measure of context recollection. We will use two different versions of the task with different and non-overlapping sets of objects at the two test sessions and the order of versions will be counterbalanced across participants.

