Spatial Task: This is a test of spatial processing, which will serve as a control task to isolate neural markers of memory engagement, versus engagement in any task with similar visuospatial qualities. Notably, spatial processing activates a network of frontoparietal including the posterior parietal cortex regions^{54,55}, allowing it to further serve as a control to isolate hippocampal network effects of TMS from the local effects of TMS on the stimulated region. In each trial of this task, participants will be shown an arrow pointing to one corner of the screen and displayed in one of four quadrants. They will be instructed to indicate by button press whether the arrow points to the corner in which it is displayed (“match,” e.g. pointing to the upper right corner in the upper right quadrant) or a different corner (“no-match,” e.g. pointing to the upper right corner in the upper left quadrant). Accuracy of match/no-match responses will be assessed. Each arrow will be presented for 4 seconds with 4 seconds between trials. In Experiment 1, TMS will occur during a 2 second cue before each trial and in Experiment 2, TMS will occur in the first 2 seconds of stimulus presentation. There will be 180 trials, interspersed with encoding trials of the memory task. We will use two different versions of the task at the two test sessions.

TMS

The parietal target will be the region of the left posterior parietal cortex with the greatest connectivity with the left hippocampus derived from the baseline resting-state fMRI session³¹. This region was chosen because of its dense connections with the hippocampus^{56,57}. Thus, stimulation of this location can modulate function of the hippocampal-cortical network^{30-36,38}.

The control target will be vertex, a commonly used active control site which does not influence neural or behavioral activity⁵⁸.

TMS targets will be marked in the participant’s anatomical MRI volume and located with a frameless stereotaxic system. If any experiment, for any reason, fails to produce useful individual targets, a literature-based location for the parietal cortex³¹ will be used as our location of stimulation. To reduce the influence of diurnal variations in the responsiveness to neuroplasticity protocols⁵⁹, we will make every effort to test subjects during the same time of day.

[figure not shown]

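### In Experiment 2 the TMS train covers the encoding EEG windows, so the site main effect and site x timing can be significant only because stimulated trials differ from no-TMS trials

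*Combined protocol and SAP*

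**What the plan says.** Section 3 sets one ERP window for both experiments, "ERP amplitude 500-700 ms after trial onset (encoding and retrieval) over parietal and occipital electrodes", and one theta/alpha window, "Power in the 4-13 Hz band 0-1000 ms after trial onset (encoding and retrieval").

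Section 4 sets the stimulation timing. In Experiment 1, "TMS will be delivered during the rest phase immediately prior to trial onsets", within a 2-second cue. For the memory task, "in Experiment 2, TMS will occur in the first 2 seconds of stimulus object presentation"; for the spatial task, "in Experiment 2, TMS will occur in the first 2 seconds of stimulus presentation". The TMS subsection says that the Experiment 2 train starts together with the trial and consists of 50 Hz triplets every 200 ms. One-third of trials carry no stimulation; their stated purpose is "to examine behavioral and neural effects in the absence of the TMS sensory artifact".

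Section 8.3.2 analyses each outcome with a 3x3 ANOVA (Objective 1: trial type and site) and a 3x3x2 ANOVA (Objective 2: timing added). Site has three levels: parietal, vertex and none. Four tests are singled out: the site main effect, trial type x site, site x timing, and the three-way interaction. The threshold is 0.025 after FDR correction. No parietal-versus-vertex contrast is named there, although hypothesis 1b in Section 8.1 is worded against vertex-TMS. Hypothesis 1e predicts no effect of parietal-TMS on spatial-trial neural activity relative to vertex-TMS and to no-TMS.

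**The concern.** A three-level site test asks whether any of parietal, vertex and none differ. During Experiment 2 encoding, the two stimulated levels have pulses inside the measurement window and the third does not. Any response to the pulses that survives processing separates stimulated trials from none, whatever the coil position and whether or not the item is later remembered. Because the pulses fall in the window only in the mid-trial experiment, the same response also produces a site x timing interaction.

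Two of the four tests that Section 8.3.2 singles out are therefore open to a significant encoding-EEG result that could be read as a TMS effect on memory activity, or as dependence on task state. In hypothesis 1e the error runs the other way: spatial trials receive the same train, so a parietal-versus-none difference could wrongly count against task specificity. The late positive posterior ERP matters most, because Section 8.2 shares alpha between it and memory performance.

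**Working it through.** **Overlap (from the documents).** Bursts fall at 0, 200, ..., 1800 ms, with pulses at +0, +20 and +40 ms (50 Hz).
- Pulses per train: 10 x 3 = 30, the last at 1800 + 40 = 1840 ms.
- In 500-700 ms: 600, 620 and 640 ms, so 3.
- In 0-1000 ms: five bursts (0 to 800 ms) x 3 = 15.
- The 5 Hz burst rate and its 10 Hz harmonic both lie inside the 4-13 Hz band.
- Experiment 1: a train starting 2000 ms before onset has its last pulse at -2000 + 1840 = -160 ms, so none in either window.
- Stim-off trials: none.
- Table 1: 30 + 30 = 60 of the 4 x 30 = 120 stimulated memory trials per participant are affected.

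**Illustration for the ERP (assumptions, not document figures).** There are 32 participants, the level is 0.025, and there is no true TMS effect. Trials per site level and experiment are 15 successful, 15 unsuccessful and 30 spatial (Table 1, with an assumed even memory split; none pools 15 + 15). Single-trial SD is 1, participant-by-site SD 0.2 and cell SD 0.115. A residual response r is added to mid-trial parietal and vertex cells; its between-participant SD is r/2. Tests are Greenhouse-Geisser F tests or t tests, with 4,000 runs per scenario.

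| Unadjusted false-positive rate | r = 0.02 | 0.05 | 0.1 | 0.2 |
|---|---|---|---|---|
| Site, Experiment 2 | 3% | 6% | 23% | 80% |
| Site, experiments pooled | 2% | 3% | 7% | 28% |
| Site x timing | 2% | 7% | 32% | 91% |
| 1e, parietal vs none, spatial, Experiment 2 | 3% | 6% | 18% | 62% |

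The 1e row can be checked by hand. At r = 0.1 the variance of the difference is 2/30 + 2(0.115²) + 2(0.2²) + 0.05² = 0.1756. The SE is √(0.1756/32) = 0.0741 and the noncentrality 0.1/0.0741 = 1.35, against a critical t of 2.36. This gives about 17%.

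At r = 0 the unadjusted tests gave 1.5-2.6%. With equal coils, trial type x site, the three-way interaction and 1b stay at about 2% throughout.

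**FDR.** Section 8.3.2 does not define the family. With Benjamini-Hochberg at 0.025, for r = 0.02/0.05/0.1/0.2:
- Within each ANOVA: Experiment 2 site 1/3/13/67%; site x timing <1/1/15/83%.
- Across four endpoints: <1/1/5/48% and 0/<1/6/66%.

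**Sensitivity.**
- At r = 0.1, a participant-by-site SD of 0 or 0.4 moves the unadjusted Experiment 2 site rate from 23% to 63% or 8%.
- At r = 0.2, a half-size response carried into Experiment 1 cuts site x timing to 32% and raises the pooled site rate to 64%.

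**Is parietal minus vertex safe?** Only if the coils evoke equal responses. For 0.1 vs 0.05, 0.2 vs 0.1 and 0.3 vs 0.1, the simple difference on Experiment 2 spatial trials gives about 6, 17 and 62%. The 1b contrast removes coil inequality if the response does not depend on later success. If it is 50% larger on forgotten trials, 1b gives 3% (0.2 at both coils), 4% (0.2 vs 0.1) and 6% (0.3 vs 0.1).

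**The case against.** The case for the plan as written is substantial.

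- **Vertex is the main control.** The improvement hypotheses are worded against vertex-TMS or pre-trial parietal-TMS, and no-TMS is an additional control. A significant three-level test does not say which levels differ. This stands as a reading of intent, but Section 8.3.2 names no contrast that carries it out.
- **Task specificity rests on the interactions.** Section 8.3.2 assigns it to trial type x site and the three-way test. This stands, if the response is additive and equal across trial types. Hypothesis 1e also names both comparators, and viewed together they would reveal a non-specific response.
- **The Objective 2 EEG comparisons are already called exploratory** in Section 4 (Primary Objective) and Section 8.1. This stands; what remains is to align Section 8.3.2, which lists them with the primary endpoints at 0.025.
- **Artifact handling is planned.** The EEG subsection provides ICA and/or other processing, plus single-trial screening. The residual may be small. But these steps target artifact and do not remove genuine sensory or cortical responses to the pulses.
- **Experiment 1 is free of pulses in both windows.** For participants with data from only one experiment, Section 4 says "those data will still be included in analysis for that experiment but excluded from any comparisons across experiments", which suggests separate analyses. Section 8.3.2 does not say whether the Objective 1 ANOVA pools.

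A reader might infer that the EEG results as a whole, or the trial's primary conclusion, are invalid. The documents do not support that: stimulation is given only at encoding, so memory performance and retrieval EEG lie outside the overlap.

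**Conclusion.** The point holds for encoding EEG that includes Experiment 2. The overlap, and which tests it exposes, follow directly from the documents: the three-level site main effect, site x timing, and the no-TMS comparison in 1e.

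The size of the error does not follow from them. The documents give no residual amplitude, variance or correlation, so the rates above show a range and are not estimates. They run from close to nominal at 0.02 SD to 80% or more at 0.2 SD unadjusted, and fall under FDR.

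Two further readings should be resisted. The rates do not carry over to theta/alpha power: it is decomposed from event-related averages, where overlapping signals do not simply add, so for power only the overlap is established. Nor does replacing no-TMS by vertex cure 1e, since parietal minus vertex is itself biased when the coils evoke unequal responses.

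Trial type x site, the three-way interaction and 1b are protected on the condition that the evoked response is additive and equal across trial types. This should be fixed before analysis; it does not call the design or the stimulation schedule into question.

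**What to change.** In Section 8.3.2:

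1. Make the confirmatory encoding-ERP test the contrast already hypothesised as 1b, (successful minus unsuccessful) x (parietal minus vertex). State its assumption that the evoked response is unrelated to later success. Give Experiment 1 alone as a sensitivity analysis.
2. For encoding EEG, treat as exploratory the three-level site main effect wherever Experiment 2 data enter, and site x timing. For Objective 2 this aligns Section 8.3.2 with Sections 4 and 8.1. State whether the Objective 1 ANOVA pools the experiments.
3. For 1e on Experiment 2 encoding EEG, do not take a parietal-versus-none difference alone as evidence against specificity. Report parietal-vertex, parietal-none and vertex-none together, rest specificity on trial type x site, and note that unequal coil responses bias parietal-vertex.
4. Optionally, report retrieval-phase EEG by encoding condition as a pulse-free supplement. It has no spatial-task comparison, so it does not test the encoding hypotheses.

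The cost is wording only, with no new data. The plan gives up any confirmatory claim about overall EEG amplitude or power during mid-trial stimulation.

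1b is also a less precise difference of differences. Under the assumptions above its SE is √(4(1/30 + 0.115²/2)/32) = 0.071 on all trials and √(4(1/15 + 0.115²)/32) = 0.100 on Experiment 1 alone. That gives 80% power at 0.025 for about 0.23 and 0.32 single-trial SD. Experiment 1 is pulse-free but not necessarily response-free, because its last pulse falls about 160 ms before onset.
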